The database includes patient demographic information, baseline clinical characteristics, indicators related to diagnosis and treatment during hospitalisation and follow-up after discharge. The platform staffs tried to follow up all discharged patients by a phone call at 1-year discharge. Telephone follow-up of the platform was conducted by platform staffs. The follow-up standards were unified, and telephone recordings were all kept. Neurologists conducted trainings at regular intervals for platform staffs and randomly checked the telephone recordings. Several studies based on this dataset were approved by the Second Affiliated Hospital of Zhejiang University Institutional Review Board (IRB) and were published in peer-reviewed journals. [\[P21-04780\]](#), [\[P21-04783\]](#), [\[P21-04784\]](#), [\[P21-04779\]](#), [\[P21-04782\]](#)

E) STUDY SIZE

There were approximately 8500 AIS patients (≥ 18 years of age) who were treated with IV rt-PA and 3200 patients who were admitted to the hospital within 4.5 hours of symptom onset and did not receive reperfusion treatment from Jan 2017 to Mar 2020.

In the China National Stroke Registry I (2007-2008), the 12-month mortality rate for post-stroke patients was approximately 14%. [\[R21-1852\]](#) For this study, it is assumed that 1-year mortality is 12% and 15% for the rt-PA treatment cohort and the cohort who did not receive reperfusion, respectively. In total, 6069 patients with a treatment ratio 2:1 are needed to observe 855 events and to detect the difference (hazard ratio=0.79) with a 2-sided alpha of 0.05 and 90% power. In addition, considering a treatment ratio 1:1 with the same assumption described above with power of 90% at a 2-sided, 5% significant level, roughly 5400 patients are needed to observe 756 events to detect the difference.

F) DATA MANAGEMENT

The data will be managed by ZSQCC. The source codes for data management and data analyses will be kept for inspection for at least 5 years after publication of the results.

Full details of the data management plan are documented in a separate NIS-Data Management and Review Plan (NIS-DMRP).

G) DATA ANALYSIS

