For the purpose of this study, analyses will generally be descriptive in nature and will be conducted using SAS statistical software (version 9.3 or higher). Descriptive data regarding patient demographic and clinical characteristics will be calculated. For categorical measures, data will include the frequency (number of cases [n]) and percentage (%) of total study patients observed in each category (N). All variables will be summarised descriptively through tabular displays of mean, median, ranges and standard deviations of continuous variables and frequency distributions of categorical variables. When necessary, continuous

variables also will be categorised into intervals, with the distribution of patients (n, N, %) for each interval provided.

The statistical analysis plan for the study is summarised below. Full details of the statistical analysis will be documented in the statistical and epidemiological analysis plan, which will be finalised before the end of data extraction.

As this is a NIS based on existing data, no formal hypothesis testing or comparisons between treatment cohorts are planned.

i. Main analysis

To account for potential confounding, the study cohorts (patients who received IV rt-PA and patients who did not receive reperfusion treatment) will be 1:1 or 2:1 matched by baseline characteristics using the propensity score matching (PSM) method. Propensity score (PS) will be derived from predicted probabilities of treatment initiation. The PSM aims to balance the 2 treatment cohorts on baseline covariates. The feasibility of PSM will be evaluated based on available sample size and descriptive results. If patient characteristics between the 2 cohorts are significantly different, i.e., less than 50% of patients in the IV rt-PA cohort can be matched to the non-reperfusion cohort based on PSM, the study design will be re-evaluated before proceeding to analysis. The Nearest Neighbour method of PSM will be used to select the matched samples. All the variables listed in the covariates will be considered. Covariates including duration of hospitalization and reasons for untreated with rt-PA are only for descriptive analysis. The distribution of baseline characteristics will be presented before and after the matching process. For baseline covariates that are not sufficiently balanced after PSM, the covariates will be included in an appropriate multivariate model to adjust for those differences.

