Baseline characteristics of patients who received IV rt-PA and who didn't receive reperfusion treatments will be described, both before and after PSM. The absolute standardised difference (ASD) between the PS-matched cohorts will be calculated, where an ASD of at least 10% ASD will be considered a meaningful difference.

In the primary analysis, all patients who received endovascular treatment will be excluded. For the primary outcome, all-cause mortality at 1-year (mRS=6), will be evaluated using from the Kaplan-Meier curve. The percentage of 1-year mortality with 95% CIs in the 2 PS-matched cohorts will be calculated separately. Cox regression models will be used to estimate the hazard ratio for the primary outcome between PS-matched cohorts.

For the secondary outcomes, descriptive summaries will be conducted in the PS-matched cohorts separately. For categorical variables including functional independence (mRS 0-2), favourable clinical outcome (mRS 0-1) and outcome of mRS 5-6, the percentage and 95% CI will be calculated. A logistic regression model will be used to calculate odds ratios for functional independence (mRS 0-2), favourable clinical outcome (mRS 0-1) and outcome of mRS 5-6. For the distribution of mRS at 1 year, an ordinal logistic regression model will be used to calculate the odds ratio and 95% CI.

The primary and secondary outcomes will be analysed using the same method described above in following subgroups:

- Baseline NIHSS score (0-4, 5-10, 11-15, 16-21 and \geq 22)
- Onset to treatment time (\leq 90 mins, 91-180 mins, and 181-270 mins)
- Age (18-80 years, $>$ 80 years)
- rt-PA dose (low dose of \sim 0.6 mg/kg, standard dose 0.9 mg/kg)

Subgroup analyses will be conducted only when the patient number of each subgroup is equal to or exceeds 6069 or 5400 based on 2:1 or 1:1 treatment ratio assumption, respectively.

iii. Safety analysis

This study is a NIS based on existing data. From safety information collecting and reporting perspective, this study will not involve individual medical record review, thus no adverse event/adverse drug reaction information is required to collect. The analysis refers to [Section ii.](#)

H) QUALITY CONTROL

The study will strictly follow BI standard operation procedures (SOPs). In addition, this study will follow key elements of the Guideline for GPP. The statistical analytic approach will be reviewed/repeated by a second analyst. The study report will be reviewed, approved and archived per BI SOP.

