4. PURPOSE AND SCOPE

This is a complete statistical and epidemiological analysis plan for the research about what are the 1-year clinical outcomes among AIS patients who were treated with IV rt-PA within 4.5 hours of symptom onset compared with those who arrived or were admitted to the hospital within 4.5 hours of symptom onset and did not receive any reperfusion treatment in a real-world clinical setting, including the 1-year all-cause mortality and neurological functional outcomes. More detailed and explicit statistical analysis methods and procedures are presented here, especially the Propensity Score Matching method.

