To account for potential confounding, the 2 cohorts will be 1:1 or 2:1 matched by baseline characteristics using the Propensity Score Matching method. The feasibility of PSM will be evaluated based on available sample size and descriptive results. If patient characteristics between the 2 cohorts are significantly different, i.e., less than 50% of patients in the IV rt PA cohort can be matched to the non-reperfusion cohort based on PSM, the study design will be re-evaluated before proceeding to analysis. The PSM aims to balance the 2 cohorts on baseline covariates. The propensity score model will include age, gender, baseline NIHSS/NIHSS categories (0-4, 5-10, 11-15, 16-21, and ≥ 22), pre-stroke mRS, medical insurance status, smoking status, hospital level, diabetes, coronary artery disease, atrial fibrillation, prior stroke/transient ischaemic attack, hypertension, anti-platelet, lipid lowering, oral anticoagulation, and time from symptom onset to hospital admission. The method of Nearest Neighbour matching will be used (a maximum caliper width equal to 0.2 of the standard deviation of the logit of the propensity score) to select the matched samples. Then we will compare the baseline characteristics of the 2 propensity-score-matched cohorts. The absolute standardized difference (ASD) between the 2 PS-matched cohorts will be calculated, where at least 0.1 ASD will be considered a significant difference. For baseline covariates that are not sufficiently balanced after PSM, they will be included in an appropriate multivariate model to adjust for those differences.

For the primary outcome, a comparison of the percentage of 1-year* all-cause mortality (mRS=6) between the 2 matched cohorts will be conducted using a Chi-square test. A Kaplan-Meier curve with log-rank test will be used to analyse the data. Cox regression models will be used to estimate hazard ratios (95% confidence interval) between the 2 matched cohorts.

For the secondary outcomes, descriptive summaries will be conducted in the PS-matched cohorts separately. For the categorical variables including functional independence (mRS 0-2), favourable clinical outcome (mRS 0-1), and mRS 5-6 at 1 year, the Chi-square test and conditional logistic regression model will be conducted. For the distribution of mRS score at 1 year, the Wilcoxon rank sum test and ordinal logistic regression model will be performed to calculate the odds ratio and 95% CI.

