Proprietary confidential information © 2021 Boehringer Ingelheim International GmbH or one or more of its affiliated companies

The primary and secondary outcomes will be analysed using the same method described above in the following subgroups:

- Baseline NIHSS score (0-4, 5-10, 11-15, 16-21 and ≥ 22)
- Onset to treatment time (≤ 90 mins, 91-180 mins, and 181-270 mins)
- Age (18-80 years, > 80 years)
- rt PA dose (low dose of ~ 0.6 mg/kg, standard dose 0.9 mg/kg)

*Note: 1 year in this analysis is defined as 12 ± 1 months.

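### The protocol's minimum per subgroup is the whole-study sample size, out of reach for all NIHSS levels (and for both age levels if controls are used once); the SAP omits it, and the comparator for onset-to-treatment and dose levels is undefined

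*Protocol*

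**What the plan says.** Protocol 9.E (Study size) gives the whole-study requirement: "In total, 6069 patients with a treatment ratio 2:1 are needed to observe 855 events and to detect the difference", at 90% power and two-sided 5%, with roughly 5400 patients and 756 events at 1:1. It puts the available data at about 8500 adults "who were treated with IV rt-PA and 3200 patients who were admitted to the hospital within 4.5 hours of symptom onset" and had no reperfusion.

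Protocol 9.G.i (Main analysis) and the abstract list four subgroup factors: NIHSS (five levels), onset-to-treatment time (three), age (two) and rt-PA dose (two). Both then add: "Subgroup analyses will be conducted only when the patient number of each subgroup is equal to or exceeds 6069 or 5400", for 2:1 and 1:1 respectively.

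SAP 11.1 lists the same factors and cut-points: "The primary and secondary outcomes will be analysed using the same method described above in the following subgroups". It sets no minimum. In the SAP the figures 6069 and 5400 appear only in section 7.1, as the study size. The amendment sections of both documents read None.

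Protocol 9.C.iii and SAP 8.3 list onset-to-treatment time and dose only for the rt-PA cohort. The SAP 11.1 propensity model ends with "lipid lowering, oral anticoagulation, and time from symptom onset to hospital admission".

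**The concern.** A number sized for the whole comparison has become an entry condition for each part of it. Several parts of one matched set cannot each be as large as a study that uses most of that set. An analyst following the protocol would leave out results that an analyst following the SAP would report, and nothing says which text governs.

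The second difficulty is independent of the first. A control has no onset-to-treatment time and no dose, so a subgroup defined by either factor contains treated patients only until someone decides which controls belong with it. That choice affects what the hazard ratio means, and the plan does not make it.

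**Working it through.** **1. The threshold is the whole-study size.** Inputs from Protocol 9.E: 15% against 12% mortality, HR 0.79, two-sided 5%, 90% power.
- Patients, two-proportion formula with pooled variance: 3 × 2030 = 6090 with two rt-PA patients per control (stated 6069) and 5450 at 1:1 (stated 5400).
- Events, Schoenfeld: D = (1.960 + 1.282)² / [p(1−p)(ln 0.79)²] = 851 for p = 2/3 (stated 855) and 757 for p = 1/2 (stated 756).

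The stated figures are reproduced closely. They are totals for one comparison.

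**2. Direction of 2:1.** The documents do not state it. The patient total fits two rt-PA patients per control better (6090, against 6171 for the reverse). The event fraction fits the reverse better: 855/6069 = 14.1%, against (2 × 12 + 15)/3 = 13.0% or (12 + 2 × 15)/3 = 14.0%. At 1:1, where direction is irrelevant, 756/5400 = 14.0% also exceeds the expected 13.5%, so the event fraction is weak evidence. Both directions are carried below.

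**3. Largest matched set against the requirement.**

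| | 1:1 | 2:1, two rt-PA per control | 2:1, two controls per rt-PA |
|---|---|---|---|
| Controls used once | 3200 + 3200 = 6400 | 6400 + 3200 = 9600 | 1600 + 3200 = 4800 |
| Controls reused, counting records | 8500 + 8500 = 17,000 | 8500 + 4250 = 12,750 | 8500 + 17,000 = 25,500 |
| Five NIHSS levels need | 5 × 5400 = 27,000 | 5 × 6069 = 30,345 | 30,345 |
| Two age levels need | 2 × 5400 = 10,800 | 2 × 6069 = 12,138 | 12,138 |

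- NIHSS fails in every column, with or without reuse.
- Age fails in every column when controls are used once. With reuse and counting records it is possible, but the records over 80 would have to be at least 5400/17,000 = 32%, 6069/12,750 = 48% or 6069/25,500 = 24% of the total.
- With controls used once, one level at most can pass. It must hold 5400/6400 = 84% of a full 1:1 set, or 6069/9600 = 63% of a full 2:1 set with two rt-PA patients per control. In the reverse direction no level can pass, since 4800 < 6069.
- If patients were counted before matching (about 11,700), NIHSS still fails. Age fails at 2:1; at 1:1 it needs 5400/11,700 = 46% over 80.
- At 1:1 with controls used once, at most 3200/8500 = 38% of rt-PA patients are matched, which already triggers the re-evaluation rule ("less than 50% of patients in the IV rt-PA cohort can be matched to the non-reperfusion cohort based on PSM").

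**4. Onset-to-treatment time and dose.** Whether the minimum blocks these depends on the missing comparator rule. If each level is matched separately and controls may serve in several levels, 1:1 needs 2700 rt-PA patients per level: 5400 for dose and 8100 for onset-to-treatment time, against 8500 available. With two rt-PA patients per control it needs 4046 per level: 8092 for dose (fits) and 12,138 for onset-to-treatment time (does not). With two controls per rt-PA patient, one level needs 4046 controls and only 3200 exist.

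**5. What the comparator choice does.** A patient treated within 90 minutes of onset arrived within 90 minutes. A control may have arrived up to 270 minutes after onset. Comparing the early level with all matched controls would therefore unbalance onset-to-admission time, a propensity-score variable. The documents give no arrival times, so the size is unknown. Purely as illustration, uniform arrivals over 0–90 minutes against 0–120, 0–180 or 0–270 minutes give standardised differences of 0.49, 1.10 or 1.55, against the plan's 0.1 limit.

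**6. Precision without the minimum.** A full set with two rt-PA patients per control has 6400 × 0.12 + 3200 × 0.15 = 1248 expected deaths. A level with an assumed 5% share and the same mortality has about 62. SE(log HR) = √(4.5/62.4) = 0.27, so the 95% interval runs from about 0.59 to 1.69 times the HR.

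**The case against.** The minimum may be a deliberate safeguard: run a subgroup only if it has the power of the main comparison. That is strict but coherent, and one large level, such as 18–80 years, might pass. This stands as far as intent goes. It does not explain why the SAP omits the rule, and a single level without its counterpart says nothing about differences between levels.

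It can also be argued that the SAP governs. The protocol says "Full details of the statistical analysis will be documented in the statistical and epidemiological analysis plan" and the SAP says "This is a complete statistical and epidemiological analysis plan". But Protocol section 10 requires the study to comply with the protocol, and neither document withdraws the minimum.

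On the comparator, the subgroup instruction follows text that begins with matching, so a fresh match per level is a fair reading. Conditional logistic regression also suggests comparison within matched sets. The Kaplan-Meier, Cox and ordinal analyses carry no such indication, so the gap remains.

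A reader might infer that age can never meet the minimum, or that no subgroup could ever be reported. The documents support neither: they do not rule out reuse of controls, and one dominant level or some dose and onset-to-treatment levels could qualify under certain readings. A reader might also infer that the plan intends to use all matched controls, or that the comparator will be picked to suit the data. The text is merely silent.

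**Conclusion.** The concern holds in this form. The minimum is the whole-study sample size. It cannot be met at all five NIHSS levels on any reading examined, nor at both age levels if each control is used once. Because the SAP orders the same analyses without it, the two documents prescribe different sets of subgroup results. The comparator for onset-to-treatment and dose levels is unspecified, and one natural choice, all matched controls, would mix arrival time into the treatment effect by an amount the documents do not allow to be calculated.

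The ceilings rest on the documents' approximate counts (8500 and 3200) and on every control being matched. The figures 9600 and 63% also assume two rt-PA patients per control. A caliper can only lower the ceilings. The primary analysis is not affected.

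**What to change.** 1. Remove the 6069/5400 minimum from Protocol 9.G.i and the abstract so that the protocol agrees with SAP 11.1, and record this as an amendment. Copying the minimum into the SAP would also align the texts, but would leave NIHSS unreportable at all levels, and age too if controls are used once.
2. Label subgroup results exploratory. Report patients and deaths by cohort for each level, the HR with 95% CI, and odds ratios with 95% CI for the secondary outcomes. For age and NIHSS, match within level (or exactly on level) so that matched sets do not straddle levels, and add a treatment-by-subgroup interaction estimate with 95% CI.
3. For onset-to-treatment time and dose, match the rt-PA patients of each level separately to the full non-reperfusion pool, using the SAP 11.1 propensity model and caliper, at the main-analysis ratio where the pool allows and otherwise 1:1. A control may serve in several levels but only once within a level. Show the levels side by side without an interaction term, because controls have no level.
4. Report standardised differences within each level, including onset-to-admission time, and apply the SAP's adjustment rule where they reach 0.1. State that the 50% re-evaluation rule applies to the main match only.

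Cost: no new data, but extra matching runs and balance tables, and a protocol amendment with IRB/IEC approval (Protocol 10.A). Small strata will have wide intervals, as the 5% example shows.

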10. PROTECTION OF HUMAN SUBJECTS

The study will be carried out in compliance with the protocol, the principles laid down in the Declaration of Helsinki, in accordance with the International Conference on Harmonisation Harmonised Tripartite Guideline for Good Clinical Practice (to the extent applicable to the NIS setting and required by local regulations), Good Epidemiological Practice, guidelines for GPP, and the relevant BI SOPs.

A) STUDY APPROVAL AND PATIENT INFORMATION

This NIS will be initiated only after all required legal documentation has been reviewed and approved by the respective IRB/IEC and Competent Authority according to national and international regulations. The same applies for the implementation of changes introduced by amendments.

B) STATEMENT OF CONFIDENTIALITY

Individual patient medical information obtained as a result of this study is considered confidential and disclosure to third parties is prohibited with the exceptions noted below. Patient confidentiality will be ensured by using patient identification code numbers.

Data generated as a result of the study need to be available for inspection upon request by the participating physicians, the sponsor's representatives, by the IRB/IEC and the regulatory authorities.

11. MANAGEMENT AND REPORTING OF ADVERSE EVENTS/ADVERSE REACTIONS

Based on current guidelines from the International Society for Pharmacoeconomics and Outcomes Research [R11-4318] and the European Medicines Agency [R13-1970], NIS such as the one described in this proposal, conducted using health care records, do not require expedited reporting of suspected adverse events/reactions. Specifically, as stated in section VI.C.1.2.1 of Guideline on Good Pharmacovigilance Practices, Module VI – Management and Reporting of Adverse Reactions to Medicinal Products, for NIS designs, which are based on use of secondary data, reporting of adverse reactions is not required. Not applicable based on the secondary use of data without any potential that any employee of BI or agent working on behalf of BI will access individually identifiable patient data.

12. PLANS FOR DISSEMINATING AND COMMUNICATING STUDY RESULTS

The rights of the investigator and of the sponsor with regard to publication of the results of this study are described in the investigator contract. As a general rule, no study results should be published prior to finalisation of the Study Report.

Boehringer Ingelheim intends to use data from this study to prepare peer-reviewed publications and other scientific communications such as abstracts, posters, and podiums presentations.

ANNEX 1. LIST OF STAND-ALONE DOCUMENTS

None.

ANNEX 2. ENCEPP CHECKLIST FOR STUDY PROTOCOLS

1.	Study title: 1-year clinical outcomes after intravenous rt-PA for Chinese AIS patients
----	---

2.	EU PAS Register® number:
3.	Study reference number (if applicable):

4. Section 1: Milestones	Yes	No	N/A	Section Number
1.1 Does the protocol specify timelines for				
1.1.1 Start of data collection ¹				6
1.1.2 End of data collection ²				6
1.1.3 Progress report(s)				NA
1.1.4 Interim report(s)				NA
1.1.5 Registration in the EU PAS Register®				6
1.1.6 Final report of study results.				6

Comments:

--

5. Section 2: Research question	Yes	No	N/A	Section Number
2.1 Does the formulation of the research question and objectives clearly explain:				7 and 8
2.1.1 Why the study is conducted? (e.g. to address an important public health concern, a risk identified in the risk management plan, an emerging safety issue)				7
2.1.2 The objective(s) of the study?				8
2.1.3 The target population? (i.e. population or subgroup to whom the study results are intended to be generalised)				9.2.2
2.1.4 Which hypothesis(-es) is (are) to be tested?				NA
2.1.5 If applicable, that there is no a priori hypothesis?				NA

Comments:

--

¹ Date from which information on the first study is first recorded in the study dataset or, in the case of secondary use of data, the date from which data extraction starts.

² Date from which the analytical dataset is completely available.

6. Section 3: Study design	Yes	No	N/A	Section Number
3.1 Is the study design described? (e.g. cohort, case-control, cross-sectional, other design)				9.1
3.2 Does the protocol specify whether the study is based on primary, secondary or combined data collection?				9.1 and 9.3.2
3.3 Does the protocol specify measures of occurrence? (e.g., rate, risk, prevalence)				9.2.2
3.4 Does the protocol specify measure(s) of association? (e.g. risk, odds ratio, excess risk, rate ratio, hazard ratio, risk/rate difference, number needed to harm (NNH))				NA
3.5 Does the protocol describe the approach for the collection and reporting of adverse events/adverse reactions? (e.g. adverse events that will not be collected in case of primary data collection)				9.7.3 and 11

Comments:

7. Section 4: Source and study populations	Yes	No	N/A	Section Number
4.1 Is the source population described?				9
4.2 Is the planned study population defined in terms of:				
4.2.1 Study time period				6
4.2.2 Age and sex				9.2.2
4.2.3 Country of origin				9.2.2
4.2.4 Disease/indication				9.2.2
4.2.5 Duration of follow-up				9.4.1
4.3 Does the protocol define how the study population will be sampled from the source population? (e.g. event or inclusion/exclusion criteria)				9.2.2

Comments:

8. Section 5: Exposure definition and measurement	Yes	No	N/A	Section Number
5.1 Does the protocol describe how the study exposure is defined and measured? (e.g. operational details for defining and categorising exposure, measurement of dose and duration of drug exposure)				9.3.1

BOEHRINGER INGELHEIM Group of Companies

Non-interventional Study Protocol BI Study Number 0135-0350

Page 34 of 41
c36821715-01

Proprietary confidential information © 2021 Boehringer Ingelheim International GmbH or one or more of its affiliated companies

8. Section 5: Exposure definition and measurement	Yes	No	N/A	Section Number
5.2 Does the protocol address the validity of the exposure measurement? (e.g. precision, accuracy, use of validation sub-study)				NA
5.3 Is exposure categorised according to time windows?				9.3.1
5.4 Is intensity of exposure addressed? (e.g. dose, duration)				9.3.3
5.5 Is exposure categorised based on biological mechanism of action and taking into account the pharmacokinetics and pharmacodynamics of the drug?				NA
5.6 Is (are) (an) appropriate comparator(s) identified?				NA

Comments:

9. Section 6: Outcome definition and measurement	Yes	No	N/A	Section Number
6.1 Does the protocol specify the primary and secondary (if applicable) outcome(s) to be investigated?				9.3.2
6.2 Does the protocol describe how the outcomes are defined and measured?				9.3.2
6.3 Does the protocol address the validity of outcome measurement? (e.g. precision, accuracy, sensitivity, specificity, positive predictive value, use of validation sub-study)				NA
6.4 Does the protocol describe specific outcomes relevant for Health Technology Assessment? (e.g. HRQoL, QALYs, DALYs, health care services utilisation, burden of disease or treatment, compliance, disease management)				NA

Comments:

10. Section 7: Bias	Yes	No	N/A	Section Number
7.1 Does the protocol address ways to measure confounding? (e.g. confounding by indication)				9.7.1
7.2 Does the protocol address selection bias? (e.g. healthy user/adherer bias)				9.2.1, 9.7, and 9.9
7.3 Does the protocol address information bias? (e.g. misclassification of exposure and outcomes, time-related bias)				9.7

BOEHRINGER INGELHEIM Group of Companies**Non-interventional Study Protocol**
BI Study Number 0135-0350Page 35 of 41
c36821715-01

Proprietary confidential information © 2021 Boehringer Ingelheim International GmbH or one or more of its affiliated companies

Comments:

--

11. Section 8: Effect measure modification	Yes	No	N/A	Section Number
8.1 Does the protocol address effect modifiers? (e.g. collection of data on known effect modifiers, sub-group analyses, anticipated direction of effect)				9.7.1

Comments:

--

12. Section 9: Data sources	Yes	No	N/A	Section Number
9.1 Does the protocol describe the data source(s) used in the study for the ascertainment of:				
9.1.1 Exposure? (e.g. pharmacy dispensing, general practice prescribing, claims data, self-report, face-to-face interview)				9.3.1 and 9.4
9.1.2 Outcomes? (e.g. clinical records, laboratory markers or values, claims data, self-report, patient interview including scales and questionnaires, vital statistics)				9.3.2
9.1.3 Covariates and other characteristics?				9.3.3
9.2 Does the protocol describe the information available from the data source(s) on:				
9.2.1 Exposure? (e.g. date of dispensing, drug quantity, dose, number of days of supply prescription, daily dosage, prescriber)				9.3.1
9.2.2 Outcomes? (e.g. date of occurrence, multiple event, severity measures related to event)				9.3.2
9.2.3 Covariates and other characteristics? (e.g. age, sex, clinical and drug use history, co-morbidity, co-medication, lifestyle)				9.3.3
9.3 Is a coding system described for:				
9.3.1 Exposure? (e.g. WHO Drug Dictionary, Anatomical Therapeutic Chemical (ATC) Classification System)				NA
9.3.2 Outcomes? (e.g. International Classification of Diseases (ICD), Medical Dictionary for Regulatory Activities (MedDRA))				NA
9.3.3 Covariates and other characteristics?				NA
9.4 Is a linkage method between data sources described? (e.g. based on a unique identifier or other)				NA

Comments:

--

BOEHRINGER INGELHEIM Group of Companies

Non-interventional Study Protocol BI Study Number 0135-0350

Page 36 of 41
c36821715-01

Proprietary confidential information © 2021 Boehringer Ingelheim International GmbH or one or more of its affiliated companies

13. Section 10: Analysis plan	Yes	No	N/A	Section Number
10.1 Are the statistical methods and the reason for their choice described?				9.7
10.2 Is study size and/or statistical precision estimated?				9.5
10.3 Are descriptive analyses included?				9.7
10.4 Are stratified analyses included?				NA
10.5 Does the plan describe methods for analytic control of confounding?				9.7.1
10.6 Does the plan describe methods for analytic control of outcome misclassification?				NA
10.7 Does the plan describe methods for handling missing data?				NA
10.8 Are relevant sensitivity analyses described?				9.7.2

Comments:

14. Section 11: Data management and quality control	Yes	No	N/A	Section Number
11.1 Does the protocol provide information on data storage? (e.g. software and IT environment, database maintenance and anti-fraud protection, archiving)				9.8
11.2 Are methods of quality assurance described?				9.10.1
11.3 Is there a system in place for independent review of study results?				NA

Comments:

15. Section 12: Limitations	Yes	No	N/A	Section Number
12.1 Does the protocol discuss the impact on the study results of:				
12.1.1 Selection bias?				9.9
12.1.2 Information bias?				9.9
12.1.3 Residual/unmeasured confounding? (e.g. anticipated direction and magnitude of such biases, validation sub-study, use of validation and external data, analytical methods).				NA

BOEHRINGER INGELHEIM Group of Companies**Non-interventional Study Protocol**
BI Study Number 0135-0350Page 37 of 41
c36821715-01

Proprietary confidential information © 2021 Boehringer Ingelheim International GmbH or one or more of its affiliated companies

15. Section 12: Limitations	Yes	No	N/A	Section Number
12.2 Does the protocol discuss study feasibility? (e.g. study size, anticipated exposure uptake, duration of follow-up in a cohort study, patient recruitment, precision of the estimates)				9.1 and 9.2

Comments:

16. Section 13: Ethical/data protection issues	Yes	No	N/A	Section Number
13.1 Have requirements of Ethics Committee/ Institutional Review Board been described?				10
13.2 Has any outcome of an ethical review procedure been addressed?				10
13.3 Have data protection requirements been described?				10

Comments:

17. Section 14: Amendments and deviations	Yes	No	N/A	Section Number
